Elevation in ALT, AST, and/or bilirubin, Grade 1 or 2 (run-in period)	
Continue cobimetinib and vemurafenib.
Elevation in ALT, AST, and/or bilirubin, Grade 3 (run-in period)	
Withhold vemurafenib. Continue cobimetinib.If event resolves to Grade 1 or better within 28 days, resume vemurafenib with dose reduced by one level. If not, discontinue patient from study.
Elevation in ALT, AST, and/or bilirubin, Grade 4 (run-in period)	
First episode:
 
Withhold cobimetinib and vemurafenib.If event resolves to Grade 1 or better within 28 days, resume cobimetinib and vemurafenib with doses reduced by one level. If not, discontinue patient from study. 
Subsequent episodes:
 
Discontinue patient from study.
Elevations in ALT, AST, and/or bilirubin during triple combination period	
ALT, AST, and bilirubin $\leq 3 \times$ ULN (triple combination period)	
Continue all study treatment.Monitor ALT, AST, and bilirubin at least weekly.

ULN = upper limit of normal.

^a If corticosteroids have been initiated, they must be tapered over ≥ 1 month to ≤ 10 mg/day oral prednisone or equivalent before atezolizumab can be resumed.

^b Atezolizumab may be withheld for a period of time beyond 12 weeks to allow for corticosteroids to be reduced to ≤ 10 mg/day oral prednisone or equivalent.

The acceptable length of the extended period of time must be based on an assessment of the benefits and risks by the investigator and in alignment with the protocol requirements for the duration of treatment and documented by the investigator. The Medical Monitor is available to advise as needed.

^c Resumption of atezolizumab may be considered in patients who are deriving benefit and have fully recovered from the immune-mediated event. The decision to re-challenge patients with atezolizumab should be based on *the* investigator's benefit–risk *assessment* and documented by the investigator (or an appropriate delegate). The Medical Monitor is available to advise as needed.

Table 3 Guidelines for Management of Patients Who Experience Specific Adverse Events (cont.)

Event	Action to Be Taken
Elevations in ALT, AST, and/or bilirubin during triple combination period (cont.)	

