ALT or AST $>3 \times$ ULN to $5 \times$ ULN in combination with bilirubin $\leq 3 \times$ ULN (triple combination period)	
Consider withholding all study treatment.Monitor ALT, AST, and bilirubin at least weekly. If values worsen, monitor at least every other day.If values have not worsened and have not resolved to $\leq 3 \times$ ULN upon re-evaluation 1–20 days after event onset, consider treatment with 1–2 mg/kg/day oral prednisone or equivalent.If values have not worsened and have not resolved to $\leq 3 \times$ ULN upon re-evaluation ≥ 21 days after event onset, initiate treatment with 1–2 mg/kg/day oral prednisone or equivalent.If values have worsened upon re-evaluation, initiate treatment with 1–2 mg/kg/day IV methylprednisolone or equivalent and convert to 1–2 mg/kg/day oral prednisone or equivalent upon improvement. If values do not improve within 48 hours after initiating corticosteroids, consider adding an immunosuppressive agent.If treatment is withheld and values resolve to $\leq 3 \times$ ULN before or within 12 weeks after initiation of corticosteroids, resume atezolizumab at fixed dose. ^{a,b}If values do not resolve to $\leq 3 \times$ ULN within 12 weeks after initiation of corticosteroids, permanently discontinue atezolizumab. ^{a,b,c}If treatment is withheld and values resolve to $\leq 3 \times$ ULN before or within 28 days after initiation of corticosteroids, resume cobimetinib and vemurafenib as follows:
If values did not worsen prior to resolution, resume cobimetinib and vemurafenib at current doses.If values worsened prior to resolution:
First Episode: Resume cobimetinib at current dose and resume vemurafenib with dose reduced by one level.Second Episode: Resume cobimetinib and vemurafenib with doses reduced by one level.Third Episode: Resume cobimetinib with dose reduced by one level and permanently discontinue vemurafenib.Fourth Episode: Permanently discontinue cobimetinib.If values do not resolve to $\leq 3 \times$ ULN within 28 days after initiation of corticosteroids, permanently discontinue cobimetinib and vemurafenib.

ULN = upper limit of normal.

- ^a If corticosteroids have been initiated, they must be tapered over \geq 1 month to \leq 10 mg/day oral prednisone or equivalent before atezolizumab can be resumed.

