ALT or AST $>5 \times$ ULN to $10 \times$ ULN in combination with bilirubin $\leq 1.5 \times$ ULN (triple combination period)	
 Withhold all study treatment. Monitor ALT, AST, and bilirubin at least every other day. If values do not improve within 48 hours, initiate treatment with 1–2 mg/kg/day IV methylprednisolone or equivalent and convert to 1–2 mg/kg/day oral prednisone or equivalent upon improvement. If values do not improve within 48 hours after initiating corticosteroids, consider adding an immunosuppressive agent. If values improve within 48 hours but subsequently worsen or do not resolve to $\leq 3 \times$ ULN within 14 days after event onset, initiate treatment with 1–2 mg/kg/day IV methylprednisolone or equivalent and convert to 1–2 mg/kg/day oral prednisone or equivalent upon improvement. If values do not improve within 48 hours after initiating corticosteroids, consider adding an immunosuppressive agent. If values resolve to $\leq 3 \times$ ULN before or within 12 weeks after initiation of corticosteroids, resume atezolizumab at fixed dose.^{a,b} If values do not resolve to $\leq 3 \times$ ULN within 12 weeks after initiation of corticosteroids, permanently discontinue atezolizumab.^{a,b,c} If values resolve to $\leq 3 \times$ ULN before or within 28 days after initiation of corticosteroids, resume cobimetinib and vemurafenib as follows: 
 First Episode: Resume cobimetinib at current dose and resume vemurafenib with dose reduced by one level. Second Episode: Resume cobimetinib and vemurafenib with doses reduced by one level. Third Episode: Resume cobimetinib with dose reduced by one level and permanently discontinue vemurafenib. Fourth Episode: Permanently discontinue cobimetinib. If values do not resolve to $\leq 3 \times$ ULN within 28 days after initiation of corticosteroids, permanently discontinue cobimetinib and vemurafenib.

ULN = upper limit of normal.

^a If corticosteroids have been initiated, they must be tapered over ≥ 1 month to ≤ 10 mg/day oral prednisone or equivalent before atezolizumab can be resumed.

^b Atezolizumab may be withheld for a period of time beyond 12 weeks to allow for corticosteroids to be reduced to ≤ 10 mg/day oral prednisone or equivalent.

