The acceptable length of the extended period of time must be based on an assessment of the benefits and risks by the investigator and in alignment with the protocol requirements for the duration of treatment and documented by the investigator. The Medical Monitor is available to advise as needed.

^c Resumption of atezolizumab may be considered in patients who are deriving benefit and have fully recovered from the immune-mediated event. The decision to re-challenge patients with atezolizumab should be based on *the* investigator's benefit–risk *assessment* and documented by the investigator (or an appropriate delegate). The Medical Monitor is available to advise as needed.

Table 3 Guidelines for Management of Patients Who Experience Specific Adverse Events (cont.)

Event	Action to Be Taken
Elevations in ALT, AST, and/or bilirubin during triple combination period (cont.)	
ALT or AST $>5 \times$ ULN to $10 \times$ ULN in combination with bilirubin $>1.5 \times$ ULN to $3 \times$ ULN or ALT or AST $\leq 10 \times$ ULN in combination with bilirubin $>3 \times$ ULN (triple combination period)	
Withhold all study treatment.Initiate treatment with 1–2 mg/kg/day IV methylprednisolone or equivalent and convert to 1–2 mg/kg/day oral prednisone or equivalent upon improvement. If values do not improve within 48 hours after initiating corticosteroids, consider adding an immunosuppressive agent.Monitor ALT, AST, and bilirubin at least every other day.If values resolve to $\leq 3 \times$ ULN within 12 weeks, resume atezolizumab at fixed dose. If not, permanently discontinue atezolizumab. ^{a,b,c}If values resolve to $\leq 3 \times$ ULN within 28 days, resume cobimetinib at current dose and resume vemurafenib with dose reduced by one level. If not, permanently discontinue cobimetinib and vemurafenib.
ALT $>10 \times$ ULN with or without elevation of AST or bilirubin or Confirmed cases of Hy's law with no identifiable cause other than study treatment (triple combination period)	
Permanently discontinue all study treatment and contact Medical Monitor. ^cInitiate treatment with 1–2 mg/kg/day IV methylprednisolone or equivalent and convert to 1–2 mg/kg/day oral prednisone or equivalent upon improvement. If values do not improve within 48 hours after initiating corticosteroids, consider adding an immunosuppressive agent.

IV = intravenous; ULN = upper limit of normal.

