- ^d Patients on a cobimetinib dose less than 60 mg will reduce by one dose level reduction (a 20-mg daily reduction), from a 40-mg daily dose to a 20-mg daily dose, and patients on a 20-mg daily dose at the time of the interruption (for LVEF decline) should discontinue cobimetinib.

Table 3 Guidelines for Management of Patients Who Experience Specific Adverse Events (cont.)

Event	Action to Be Taken
Rhabdomyolysis or CPK elevation	
General guidance	
 Consider withholding cobimetinib while investigating etiology. Continue atezolizumab and vemurafenib. Assess patient for any history of strenuous physical activity, blunt trauma, or recent intramuscular injections. Evaluate for cardiac injury and rhabdomyolysis. If evidence of clinically significant cardiac injury or rhabdomyolysis, consider permanent discontinuation of cobimetinib.
Asymptomatic CPK elevation, Grade 1, 2, or 3	
 Continue all study treatment.
Rhabdomyolysis or symptomatic CPK elevation, Grade 1, 2, or 3	
 Withhold cobimetinib. Continue atezolizumab and vemurafenib. If event improves by at least one grade within 28 days, resume cobimetinib with dose reduced by one level. If not, permanently discontinue cobimetinib.
Rhabdomyolysis or CPK elevation (symptomatic or asymptomatic), Grade 4	
 Withhold cobimetinib. Continue atezolizumab and vemurafenib. If event improves to Grade ≤ 3 within 28 days, resume cobimetinib with dose reduced by one level. If not, permanently discontinue cobimetinib.
Grade 3 or 4 or intolerable Grade 2 treatment-related toxicities not described above	
 Withhold all study treatment. If event resolves to Grade 1 or better within 12 weeks, resume atezolizumab at fixed dose. If not, permanently discontinue atezolizumab.^{a,b,c} If event resolves to Grade 1 or better within 28 days, resume cobimetinib and vemurafenib with doses reduced by one level. If not, permanently discontinue cobimetinib and vemurafenib.

CPK = creatine phosphokinase.

^a If corticosteroids have been initiated, they must be tapered over ≥ 1 month to ≤ 10 mg/day oral prednisone or equivalent before atezolizumab can be resumed.

^b Atezolizumab may be withheld for a period of time beyond 12 weeks to allow for corticosteroids to be reduced to ≤ 10 mg/day oral prednisone or equivalent.

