5.3.5.7 Abnormal Liver Function Tests

The finding of an elevated ALT or AST ($> 3 \times$ baseline value) in combination with either an elevated total bilirubin ($> 2 \times$ ULN) or clinical jaundice in the absence of cholestasis or other causes of hyperbilirubinemia is considered to be an indicator of severe liver injury (as defined by Hy's law). Therefore, investigators must report as an adverse event the occurrence of either of the following:

- Treatment-emergent ALT or AST $> 3 \times$ baseline value in combination with total bilirubin $> 2 \times$ ULN (of which $\geq 35\%$ is direct bilirubin)
- Treatment-emergent ALT or AST $> 3 \times$ baseline value in combination with clinical jaundice

The most appropriate diagnosis or (if a diagnosis cannot be established) the abnormal laboratory values should be recorded on the Adverse Event eCRF (see Section [5.3.5.2](#)) and reported to the Sponsor immediately (i.e., no more than 24 hours after learning of the event), either as a serious adverse event or an [REDACTED] (see Section [5.4.2](#)).

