The following are general recommendations for management of any other adverse events that may occur and are not specifically listed in the following subsections.

- *Patients and family caregivers should receive timely and up-to-date information about immunotherapies, their mechanism of action, and the clinical profile of possible immune-related adverse events prior to initiating therapy and throughout treatment and survival follow-up. There should be a high level of suspicion that new symptoms are treatment related.*
- *In general, atezolizumab therapy should be continued with close monitoring for Grade 1 toxicities, with the exception of some neurologic toxicities.*
- *Consider holding atezolizumab for most Grade 2 toxicities and resume when symptoms and/or laboratory values resolve to Grade 1 or better. Corticosteroids (initial dose of 0.5–1 mg/kg/day of prednisone or equivalent) may be administered.*
- *For Grade 2 recurrent or persistent (lasting for more than 5 days) events, treat as a Grade 3 event.*
- *Hold atezolizumab for Grade 3 toxicities and initiate treatment with high-dose corticosteroids (1–2 mg/kg/day prednisone or equivalent). Corticosteroids should be tapered over 1 month to 10 mg/day oral prednisone or equivalent, before atezolizumab can be resumed. If symptoms do not improve within 48 to 72 hours of high-dose corticosteroid use, other immunosuppressants may be offered for some toxicities.*
- *In general, Grade 4 toxicities warrant permanent discontinuation of atezolizumab treatment, with the exception of endocrinopathies that are controlled by hormone-replacement therapy.*

The investigator should consider the benefit–risk balance for a given patient prior to further administration of atezolizumab. Resumption of atezolizumab may be considered *in patients who are deriving benefit and have fully recovered from the immune-mediated event*. The decision to re-challenge patients with atezolizumab

Appendix 10
Risks Associated with Atezolizumab
and Guidelines for Management of Adverse Events Associated
with Atezolizumab (cont.)

should be based on *the investigator's assessment of the benefits and risks* and documented by the investigator. The Medical Monitor is available to advise as needed.

MANAGEMENT GUIDELINES

PULMONARY EVENTS

Management guidelines for pulmonary events are provided in Section [5.1.5.4](#).

HEPATIC EVENTS

Management guidelines for hepatic events are provided in Section [5.1.5.4](#).

GASTROINTESTINAL EVENTS

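### In the triple-combination liver rows of Table 3, AST above 10 × ULN triggers nothing by itself, so a worse AST can lead to a weaker instruction

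*Protocol*

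**What the plan says.** Protocol Section 5.1.5.4, Table 3, grades the response to liver abnormalities in the triple combination period by multiples of ULN:

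- **ALT, AST and bilirubin all ≤3:** continue treatment.
- **ALT or AST >3 to 5, bilirubin ≤3:** "Consider withholding all study treatment", and "Monitor ALT, AST, and bilirubin at least weekly. If values worsen, monitor at least every other day". If values do not worsen, oral prednisone is optional up to day 20 and required from day 21. If treatment was held, both oral drugs then restart at the current dose.
- **ALT or AST >5 to 10, bilirubin ≤1.5:** "Withhold all study treatment. Monitor ALT, AST, and bilirubin at least every other day". IV methylprednisolone follows if there is no improvement within 48 hours. In a first episode vemurafenib restarts one level lower and cobimetinib at the current dose.
- **ALT or AST >5 to 10 with bilirubin >1.5 to 3, or ALT or AST ≤10 with bilirubin >3:** withhold everything and start IV methylprednisolone.
- **ALT >10** × "ULN with or without elevation of AST or bilirubin", or confirmed Hy's law: stop all study treatment permanently.

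Three other provisions bear on the point. The last general row of Table 3 withholds all treatment for Grade 3 or 4 "treatment-related toxicities not described above". The run-in liver rows name AST at every grade, up to "Elevation in ALT, AST, and/or bilirubin, Grade 4 (run-in period"). Section 5.3.5.7 defines the Hy's law screen as ALT or AST above 3 × baseline "in combination with either an elevated total bilirubin" (above 2 × ULN) or clinical jaundice.

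**The concern.** AST has equal standing with ALT in every band from 3 to 10 × ULN and then drops out of the top row. A patient whose AST moves past 10 × ULN therefore leaves the bands AST could trigger without entering another. If ALT is between 3 and 5 × ULN, the only row still matched is the mildest one that considers a hold. If ALT is lower still, no liver row is matched.

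A toxicity table should not give a weaker instruction for a worse value. The protocol's benefit-risk section (1.5.3) lists liver laboratory abnormalities and hepatotoxicity among the overlapping toxicities of the three drugs. No other rule closes the gap: in Appendix 10, "Management guidelines for hepatic events are provided in Section" 5.1.5.4, which is this same table.

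**Working it through.** No sample size, power or alpha figure is involved. The check codes the five triple-combination rows exactly as printed, as conditions on (ALT, AST, bilirubin) in multiples of ULN, and lists the rows each first-recorded value matches.

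**Direct comparison, ALT 4 and bilirubin 1**

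- AST 8: matches the >3 to 5 row through ALT and the >5 to 10 row through AST. The second is a mandatory hold.
- AST 15: matches the >3 to 5 row through ALT and nothing else. AST 15 is outside >3 to 5 and >5 to 10, bilirubin is not above 3, and ALT is not above 10.

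**Twelve cases: AST 15 or 25; ALT 2, 4 or 7; bilirubin 1 or 2**

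Bilirubin is not above 2 × ULN, so the laboratory limb of the Hy's law screen is not met; absence of jaundice is assumed.

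| ALT | AST 8 | AST 15 or 25 | Cases with AST 15 or 25 |
|---|---|---|---|
| 2 | mandatory hold | no liver row | 4 |
| 4 | mandatory hold (also matches the optional row) | optional hold only | 4 |
| 7 | mandatory hold | mandatory hold, triggered by ALT | 4 |

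With AST 8, all 6 ALT and bilirubin pairs reach a mandatory hold. With AST 15 or 25, 4 of 12 do, and only because of ALT.

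**Cases outside the gap**

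- ALT >10 (for example 12, 15, 1) is a permanent stop.
- Bilirubin 4 with ALT 2, 4 or 7 and AST 15 or 25 is a hold with IV steroid.
- Bilirubin 2.5 is set aside. Entry requires AST ≤2 × ULN (Section 4.1.1), so AST 15 is at least 15 / 2 = 7.5 × baseline. That meets the numerical Hy's law screen and is a permanent stop if confirmed.

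**Grid check**

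ALT and AST each in {1, 2, 3, 4, 5, 6, 8, 10, 12, 25} and bilirubin in {0.5, 1, 1.5, 2, 3, 4, 8} give 10 × 10 × 7 = 700 points. Leaving Hy's law aside, as it needs confirmation, the unmatched points are exactly those with ALT ≤3, AST >10 and bilirubin ≤3: 3 × 2 × 5 = 30. Six of these have bilirubin 3 and would meet the numerical Hy's law screen; the other 24 would not. A further 2 × 2 × 5 = 20 points (ALT 4 or 5, AST 12 or 25, bilirubin ≤3) match the optional-hold row alone.

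If the rows are keyed on the higher of ALT and AST and a row is added for values above 10, all 700 points fall in exactly one row.

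**The case against.** The strongest reply is that the optional-hold result depends on a reading the table does not settle. Read literally, the rows overlap: 142 of the 700 grid points match two rows with different actions. For example, ALT 12, AST 4, bilirubin 1 matches both the optional hold and the permanent stop. Bands that overlap this much only work if the worse value governs. On that rule AST 15 is not described by any liver row, and the general Grade 3 or 4 row withholds all treatment. That row's restart, with both oral drugs one level down, is also more cautious than a first episode in the >5 to 10 row. It lacks a required call to the Medical Monitor, but so do the >5 to 10 rows, so this does not count against it.

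Other safeguards exist. Section 4.5 allows dosing only when local laboratory values are acceptable. Section 4.6.2 requires discontinuation for any condition judged to jeopardise safety. Section 5.1.5.4 says the table does not replace clinical judgment. The optional row also escalates if values worsen. An ALT-only permanent stop may be intended, because AST can rise from muscle and Table 3 has separate CPK rows.

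Much of this softens the consequence, but it does not remove the defect. The higher-enzyme rule is nowhere written. The general row has no liver monitoring interval or steroid step, and it applies only if the event is judged treatment-related and Grade 3 or 4. The judgment clauses apply equally at AST 8, so they do not explain the reversed order. The escalation clause needs further worsening, which a stable AST of 15 does not show. Muscle origin could justify omitting AST from the permanent stop. It does not explain why AST forces a hold at 8 × ULN and not at 15.

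**Conclusion.** The concern holds and should be fixed. As printed, no triple-combination liver row is triggered by AST above 10 × ULN itself. With bilirubin ≤3 × ULN and Hy's law not confirmed, a first such value is literally an optional hold when ALT is >3 to 5 × ULN, and matches no liver row when ALT is ≤3 × ULN.

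The first result assumes that the lower ALT may place the patient; if the higher enzyme governs, both cases pass to the general row. Reliance on the general row assumes Grade 3 or 4, because the protocol does not print the CTCAE cut-offs. The case and grid counts describe the logic of the table and are not estimates of how many patients are affected; the documents give no such frequency. Patients already on hold and patients in run-in are unaffected.

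**What to change.** State in Table 3 that the higher of ALT and AST decides the row. Place AST >10 × ULN with ALT ≤10 × ULN in a row carrying at least the mandatory hold of all study treatment, the every-other-day monitoring and the steroid steps of the >5 to 10 × ULN rows.

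Two choices belong to the medical team: whether this group should instead join the permanent-discontinuation row (ALT or AST >10 × ULN), and whether AST of proven muscle origin should be managed under the CPK rows.

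The cost is a wording edit to Table 3, with no new test, analysis or change in sample size. The possible downside is a few more holds, which are reversible, for AST rises of muscle origin.

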5.1.2 Risks Associated with Cobimetinib

The following adverse events are classified as identified risks associated with cobimetinib: serous retinopathy, left ventricular dysfunction, photosensitivity (when administered with vemurafenib), severe hemorrhage, rhabdomyolysis, and pneumonitis. The following adverse events are classified as potential risks for cobimetinib: severe hepatotoxicity (Grade ≥ 3), impaired female fertility, and teratogenicity and developmental toxicity. In addition, there is the possibility of drug-drug interactions in patients treated with cobimetinib (see Sections 4.4.2–4.4.4 for details). Refer to Section 6 of the Cobimetinib Investigator's Brochure for a detailed description of all anticipated risks for cobimetinib.

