5.1.2.1 Serous Retinopathy

Serous retinopathy (fluid accumulation within the layers of the retina) has been observed in patients treated with MEK inhibitors, including cobimetinib (Flaherty et al. 2012). Manifestations of serous retinopathy include visual disturbances, findings of retinal detachment, and retinopathy. Serous retinopathy events may also be asymptomatic.

To address serous retinopathy with cobimetinib treatment, all patients are required to undergo a baseline ophthalmologic examination to evaluate for risk factors for neurosensory retinal detachment. Patients will also undergo complete ophthalmologic examinations at specified timepoints throughout the study and as clinically indicated if a patient notes any visual disturbances. Details regarding baseline and subsequent ophthalmologic examinations are provided in Section 4.5.6.2.

Guidelines for management of patients who develop serous retinopathy are provided in Section 5.1.5.3 (see Table 3).

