The acceptable length of the extended period of time must be based on an assessment of the benefits and risks by the investigator and in alignment with the protocol requirements for the duration of treatment and documented by the investigator. The Medical Monitor is available to advise as needed.

^c Resumption of atezolizumab may be considered in patients who are deriving benefit and have fully recovered from the immune-mediated event. The decision to re-challenge patients with atezolizumab should be based on *the* investigator's benefit–risk *assessment* and documented by the investigator (or an appropriate delegate). The Medical Monitor is available to advise as needed.

Table 3 Guidelines for Management of Patients Who Experience Specific Adverse Events (cont.)

Event	Action to Be Taken
Ocular toxicity (cont.)	
Potential immune-mediated ocular toxicity (e.g., uveitis, retinal events), Grade 2	
Withhold atezolizumab and vemurafenib. Continue cobimetinib.Patient referral to ophthalmologist is strongly recommended.Initiate treatment with topical corticosteroid eye drops and topical immunosuppressive therapy.If event resolves to Grade 1 or better within 12 weeks, resume atezolizumab. If not, permanently discontinue atezolizumab and contact the Medical Monitor.^{a,b,c}If event resolves to Grade 1 or better within 28 days, resume vemurafenib with dose reduced by one level. If not, permanently discontinue vemurafenib.
Potential immune-mediated ocular toxicity (e.g., uveitis, retinal events), Grade 3 or 4	
Permanently discontinue atezolizumab and contact Medical Monitor. ^c Withhold cobimetinib and vemurafenib.Refer patient to ophthalmologist.Initiate treatment with 1–2 mg/kg/day oral prednisone or equivalent.If event resolves to Grade 1 or better, taper corticosteroids over ≥ 1 month.If event resolves to Grade 1 or better within 28 days, resume cobimetinib at current dose and resume vemurafenib with dose reduced by one level. If not, permanently discontinue cobimetinib and vemurafenib.

^a If corticosteroids have been initiated, they must be tapered over ≥ 1 month to ≤ 10 mg/day oral prednisone or equivalent before atezolizumab can be resumed.

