^b Atezolizumab may be withheld for a period of time beyond 12 weeks to allow for corticosteroids to be reduced to ≤ 10 mg/day oral prednisone or equivalent. The acceptable length of the extended period of time must be based on *the investigator's benefit–risk assessment* and in alignment with the protocol requirements for the duration of treatment and documented by the investigator. The Medical Monitor is available to advise as needed.

^c Resumption of atezolizumab may be considered in patients who are deriving benefit and have fully recovered from the immune-mediated event. The decision to re-challenge patients with atezolizumab should be based on *the investigator's benefit–risk assessment* and documented by the investigator. The Medical Monitor is available to advise as needed.

Table 3 Guidelines for Management of Patients Who Experience Specific Adverse Events (cont.)

Event	Action to Be Taken	
Ocular toxicity (cont.)		
Other ocular toxicity (i.e., not immune related)	
Withhold cobimetinib and vemurafenib. Continue atezolizumab.Refer patient to ophthalmologist. 
Retinal vein occlusion:
 
Permanently discontinue cobimetinib and vemurafenib. 
Serous retinopathy, Grade 1:
 
Resume cobimetinib and vemurafenib at current doses.Continue ophthalmology follow-up. 
Serous retinopathy, Grade 2 or 3:
 
Resume vemurafenib at current dose.If event resolves to Grade 1 or better within 28 days, resume cobimetinib with dose reduced by one level. If not, permanently discontinue cobimetinib. 
Serous retinopathy, Grade 4:
 
Permanently discontinue cobimetinib. Withhold vemurafenib.If event resolves to Grade 1 or better within 28 days, reduce vemurafenib with dose reduced by one level. If not, permanently discontinue vemurafenib. 
All other ocular events, Grade 1:
 
Resume cobimetinib and vemurafenib at current doses. 
All other ocular events, Grade 2, 3, or 4:
 
If event resolves to Grade 1 or better within 28 days, resume cobimetinib and vemurafenib at current doses. If not, permanently discontinue cobimetinib and vemurafenib.	

^a If corticosteroids have been initiated, they must be tapered over \geq 1 month to \leq 10 mg/day oral prednisone or equivalent before atezolizumab can be resumed.

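### Table 3 tells sites to continue cobimetinib in a Grade 2 retinal event whose cause is not yet known, although serous retinopathy is an identified cobimetinib risk

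*Protocol*

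**What the plan says.** The row in question is headed "Potential immune-mediated ocular toxicity (e.g., uveitis, retinal events), Grade 2". Its first drug instruction is "Withhold atezolizumab and vemurafenib. Continue cobimetinib". On specialist input it says "Patient referral to ophthalmologist is strongly recommended". It starts topical steroid and immunosuppressive eye treatment, and its 28-day rule acts on vemurafenib: "If event resolves to Grade 1 or better within 28 days, resume vemurafenib with dose reduced by one level. If not, permanently discontinue vemurafenib". Persistent Grade 1 events in the same category are passed up to this row.

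The other ocular row is limited to events that are not immune related. It opens with "Withhold cobimetinib and vemurafenib. Continue atezolizumab" and directs referral outright. Serous retinopathy and retinal vein occlusion are named only there. For Grade 2 or 3 serous retinopathy, vemurafenib is resumed at the current dose and the 28-day rule acts on cobimetinib: "If event resolves to Grade 1 or better within 28 days, resume cobimetinib with dose reduced by one level. If not, permanently discontinue cobimetinib".

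Protocol Section 5.1.2 lists among events "classified as identified risks associated with cobimetinib: serous retinopathy", and Section 5.1.2.1 adds: "Serous retinopathy events may also be asymptomatic".

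**The concern.** A site facing a new Grade 2 retinal finding must act before the cause is settled. The potential immune-mediated heading needs only a possible immune cause, and it names retinal events. The competing heading needs an immune cause to be ruled out. Read literally, the undiagnosed patient lands in the row that keeps cobimetinib going.

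The protocol itself expects attribution to be difficult. Section 1.5.3 lists ocular events among the overlapping toxicities of the three drugs, and investigators do not know whether the infusion is atezolizumab or placebo (Section 4.2). What is at stake is patient safety: continued dosing with a drug known to cause one of the diagnoses still under consideration. Interpretation of the efficacy endpoints is not at issue.

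**Working it through.** No arithmetic applies. The check is a comparison of the two rows, followed by a search for text that would override the first.

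| Table 3 element | Potential immune-mediated, Grade 2 | Not immune related |
|---|---|---|
| Cobimetinib, first step | continue | withhold |
| Atezolizumab or placebo, first step | withhold | continue |
| Vemurafenib, first step | withhold | withhold |
| Ophthalmology referral | strongly recommended | directed |
| Drug stopped if unresolved at 28 days | vemurafenib (atezolizumab has its own 12-week rule) | cobimetinib, for Grade 2 or 3 serous retinopathy |

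1. *First instructions.* They are opposite for two of the three drugs. Only vemurafenib is treated alike.

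2. *Which drug is kept.* Of the risk lists shown in Sections 5.1.1, 5.1.2 and 5.1.3, only the cobimetinib list has serous retinopathy as an identified risk. Holding vemurafenib is not an empty step, because uveitis is an identified vemurafenib risk. But the one drug left running is the one tied to serous retinopathy.

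3. *Text that might override the row.*
   - Section 5.1.5.3 allows cobimetinib to be suspended for toxicity considered related. That is a permission, not a direction.
   - Section 5.1.5.4 sends interruptions to the drug judged the primary cause. It gives no default when the cause is unknown. It also says that Table 3 does not replace clinical judgment.
   - The Table 3 catch-all row, which withholds everything, is confined to toxicities not covered elsewhere in the table.
   - Appendix 10 returns ocular events to Section 5.1.5.4.

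   None of these directs a cobimetinib hold while the cause is open.

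4. *Consistency with the rest of Table 3.* The non-immune row holds first and then acts on the diagnosis; even for Grade 1 serous retinopathy the hold comes before resumption. The Grade 3 or 4 potential immune-mediated row withholds cobimetinib and vemurafenib. Grade 2 colitis and Grade 2 pancreatitis withhold all study treatment. The table is not uniform, however: the Grade 2 pulmonary row only asks the site to consider withholding cobimetinib.

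5. *How long the gap lasts.* Patients are asked about vision changes at each physical examination (Section 4.5.3), and toxicity is assessed before each dose (Section 4.5). Visual disturbance leads to a complete ophthalmologic examination as clinically indicated (Section 5.1.2.1). That examination must be done by an ophthalmologist and includes OCT (Section 4.5.6.2). Once serous retinopathy or retinal vein occlusion is diagnosed, the non-immune row governs.

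**The case against.** The strongest reply is that the gap has little practical content. Calling an event retinal usually presupposes that someone has examined the retina. An asymptomatic event would normally be found at an ophthalmologic examination, so the specialist and the OCT are already involved. Section 5.3.4 presumes relatedness unless another cause is shown, drug by drug, so suspension of cobimetinib is open to the site at once. Continuing one agent may also be deliberate: the row for Grade 3 or 4 amylase or lipase elevation has the same pattern of holding the other two drugs and continuing cobimetinib.

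Most of this stands as a limit on size. It largely answers the referral half of the concern, and it makes a long undiagnosed interval unlikely. It does not remove the default. Where the row speaks to cobimetinib it says continue, and the counter-texts permit a hold without calling for one.

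Three stronger readings do not hold:

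- *Four weeks of unchecked dosing.* A reader might infer this from the 28-day clock. In this row, that clock is the deadline for resuming or stopping vemurafenib. It is not the first reassessment, and toxicity is assessed before each dose.
- *Conflicting instructions for diagnosed serous retinopathy or retinal vein occlusion.* Both are named only in the non-immune row, so there is no conflict.
- *Sites barred from holding cobimetinib.* Section 5.1.5.4 leaves room for judgment, and Section 5.1.5.3 permits suspension.

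Section 5.1.4, on risks of combined use, is redacted. The statement that nothing overrides the row therefore refers to visible text only. Section 5.1 places the management rules in Section 5.1.5, whose ocular rows are visible.

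**Conclusion.** The point holds as a minor safety improvement. At Grade 2, the row that fits a retinal event of undetermined cause directs that cobimetinib continue, while the row that would apply to the main cobimetinib-related diagnosis withholds it first. The exposure is confined to the interval before diagnosis, which should be short. Nothing is claimed at Grade 3 or 4. Nor is anything claimed for uveitis with a clear picture, where holding atezolizumab and vemurafenib may be the intended choice.

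The conclusion rests on two assumptions: that a site reads the row headings as written when the cause is open, and that the redacted section contains no interim dosing rule. With no ocular event frequency in the documents, the number of patients affected cannot be estimated.

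**What to change.** Change the Grade 2 potential immune-mediated row only, and leave Grade 3 or 4 as it is. Add:

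*For a Grade 2 retinal event of undetermined cause, also withhold cobimetinib until a prompt ophthalmologic examination, including OCT, has been done. If serous retinopathy or retinal vein occlusion is found, follow the row for other ocular toxicity. If both are excluded, resume cobimetinib at the current dose and continue under this row.*

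The last sentence matters: without it the hold would have no end when no cobimetinib-related diagnosis is made. The clinical cost is that a patient with advanced melanoma is briefly off all three study drugs until the examination. That should fall well within the 28 days for which Section 5.1.5.3 lets cobimetinib be withheld for toxicity before discontinuation is considered. The instruction is the same in both arms, so blinding is unaffected, and endpoints and data collection do not change.
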